3.2.1 Secondary Clinical Efficacy Endpoints

1. Occlusive material burden using the Venous Volumetric Index (VVI) Score¹¹, measured at Baseline and Post-EkoSonic® Study Treatment Procedure, both as a continuous measure and as a binary variable for achievement of a ≥ 5 point reduction from Baseline to Post-Procedure.
2. Change in Villalta score from Baseline to 90 days, 180 days, and 365 days Post-EkoSonic® Study Treatment Procedure, both as a continuous measure and as a binary variable for having achieved a ≥ 4 point reduction from Baseline.
3. Absence of re-occlusion at 365 days of the treated segment, as documented by duplex imaging.
4. Change in SF-36 Quality of Life (QoL) and Physical Component Summary (PCS), CEAP classification, VEINES-QOL, and VCSS from Baseline to 30, 90, 180 and 365 days Post-EkoSonic® Study Treatment Procedure.
5. Symptomatic PTS-induced admission to emergency room or unplanned visit to physician office or hospitalization from Post-EkoSonic® Study Treatment Procedure up to 365 days thereafter
6. Time from starting initial thrombolytic infusion to discharge from hospital

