4.5 Subject Withdrawal

Subjects may withdraw from participation at any time during the clinical study. All data collected prior to withdrawal shall remain part of the study. Every effort shall be made to encourage the subject to remain in the trial. If the subject declines, determine and document the reason for withdrawal.

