6.0 STATISTICAL ANALYSIS

6.1. Analysis Subject Sets, Evaluable Subjects and Missing Data Handling Convention

Efficacy Evaluable Segments are defined as DVT segments from enrolled subjects which: (a) were successfully crossed and received EkoSonic® Treatment, and (b) had Villalta scores available at both Baseline and 30 days Post-EkoSonic® Treatment visit. The **Efficacy Segment Set** includes all efficacy evaluable segments and will be used for all segment specific efficacy analyses. A treated segment that received a revascularization procedure within 30 days Post-EkoSonic® Treatment will be regarded as a failure for the primary efficacy endpoint, i.e. without a ≥ 4 -point reduction in Villalta score from Baseline to 30 days Post-EkoSonic® Treatment.

Efficacy Evaluable Subjects are defined as enrolled subjects for whom at least one affected segment: (a) was successfully crossed and received EkoSonic® Treatment, and (b) had Villalta scores available at both Baseline and 30 days Post-EkoSonic® Treatment visit. The **Efficacy Subject Set** includes all efficacy evaluable subjects and will be used for all subject specific efficacy analyses such as for quality of life measures.

Safety Subject Set

Safety evaluable subjects are defined as enrolled subjects for whom the EkoSonic® Treatment was initiated, i.e. venous access attempted for catheter introduction. The **Safety Subject Set** includes all safety evaluable subjects and will be used for all safety analyses.

Missing data will not be imputed for the primary efficacy and safety analyses. However sensitivity analyses may be performed to assess the robustness of study results with respect to missing data.

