6.2. Statistical Analysis Plan

6.2.1 General Methodology

For baseline demographics and subject characteristics, continuous measures will be summarized as mean, standard deviation, median, minimum and maximum. Categorical data will be summarized as frequencies and percentages for each data category. As appropriate, characteristics of affected segments may be similarly summarized.

For segment specific efficacy endpoints of interest, the analysis unit will be treated segment as opposed to subject. That is, assuming no missing data, subjects with bilateral DVTs will have two segments for analysis. Efficacy results will be summarized for the Efficacy Segment Set at each measurement time point. For changes from baseline at follow-up time points, continuous measures will be summarized as mean, standard deviation, median, minimum, maximum. Categorical outcomes will be summarized in two-way tables. All statistical analyses will take into account the repeated measures nature of multiple segments per subject. With subject as a random effect, the SAS GLIMMIX procedure will generally be used to evaluate the statistical significance for changes from baseline.

Analysis for subject specific efficacy measures such as SF-36 will be performed on the Evaluable Subject Set with subject as the analysis unit. Statistical significance for changes from baseline will be assessed by t-test or a nonparametric test appropriate for the data distribution.

Further analysis details will be described in the Statistical Analysis Plan.

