6.2.2 Efficacy

Efficacy analyses will be performed on the Efficacy Segment Set or Efficacy Subject Set as appropriate for the nature of the data.

Primary Clinical Efficacy Analysis:

The 30 day Villalta score change from Baseline will be analyzed as a binary variable for a segment's status as having achieved a ≥ 4 point reduction or not. Study success will be defined by $\geq 50\%$ of the efficacy evaluable segments achieving at least a 4 point reduction. In addition, as a continuous measure, change in Villalta score from Baseline to 30 day Post-EkoSonic® Treatment will also be summarized and analyzed as described above in 6.2.1 General Methodology.

Primary Technical Efficacy Analysis:

The change in blood flow calculated by time to washout in the affected segment from Baseline and Post-EkoSonic® Treatment will be analyzed as a continuous measure. A statistically significant (2-sided $p < 0.05$) improvement in flow rate, i.e. reduction in time to washout, will be considered a success for the study.

Secondary Efficacy Analyses:

For all secondary efficacy endpoints described in Section 3.2.1, i.e. VVI score change from Pre- EkoSonic® Treatment to Post-Treatment, Villalta score change from Baseline to 90, 180, and 365 days, re-occlusion rate up to 365 days, change from Baseline to all follow-up time points for SF-36 QOL and PCS component scores, CEAP classification, and VCSS, occurrences of symptomatic PTS-induced admission to emergency room or unplanned visit

to physician office or hospitalization from post EkoSonic® Treatment up to 365 days thereafter, time from starting initial thrombolytic infusion to discharge from hospital, analyses will be performed as described above in 6.2.1 General Methodology. For symptomatic PTS-induced healthcare utilization, time to event analyses will be performed for days from EkoSonic® Treatment to first occurrence for each of (a) admission to emergency room, (b) unplanned visit to physician office, and (c) hospitalization.

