6.2.3 Safety Analysis

Safety analyses will be performed for the Safety Subject Set.

For the primary safety analysis, the number and percentage of subjects with major bleeding within 72 hours of initiation of EkoSonic® Treatment will be reported with a 95% Wilson confidence interval.

Secondarily, the frequencies and proportions of subjects with symptomatic PE (diagnosed using CTPA, SPECT VQ, etc.) during hospitalization for the study procedure, and death during the 365 day follow-up period will be reported with 95% confidence intervals.

In addition, adverse events experienced will be mapped to standard terms and summarized. For a given event, the frequency and proportion of subjects reporting it will be tabulated according to the worst severity experienced. Separate tables will be constructed for (a) all reported events, (b) events judged as related to the study procedure/device/medications, and (c) SAEs.

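### One-year death is a crude proportion that withdrawals bias low; one-year re-occlusion is defined two ways and the direction of any bias is undetermined

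*Protocol*

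**What the plan says.** **Death.** Protocol section 6.2.3 covers in-hospital pulmonary embolism and one-year death in a single sentence. It plans "the frequencies and proportions of subjects with symptomatic PE" during the index hospitalization and adds that "death during the 365 day follow-up period will be reported with 95% confidence intervals". Section 6.1 fixes the denominator: the Safety Subject Set, meaning everyone in whom venous access was attempted, "includes all safety evaluable subjects and will be used for all safety analyses".

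**Withdrawal.** Section 4.5 states: "Subjects may withdraw from participation at any time during the clinical study". Data collected up to that point are kept. The schedule of assessments ends with an early-termination visit, and no contact or vital-status check after it is described.

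**Re-occlusion.** Section 3.2.1 defines the endpoint as "Absence of re-occlusion at 365 days of the treated segment, as documented by duplex imaging". Section 6.2.2 lists the analysis as "re-occlusion rate up to 365 days" and refers it to section 6.2.1, where "Categorical outcomes will be summarized in two-way tables" and efficacy results are summarized by measurement time point. The set is the Efficacy Segment Set, which "includes all efficacy evaluable segments and will be used for all segment specific efficacy analyses". It is limited to segments that were crossed, treated and scored on the Villalta scale at Baseline and Day 30.

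**Time-to-event methods.** Section 6.2.2 plans these for one 365-day outcome only, PTS-induced healthcare use.

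**The concern.** Pulmonary embolism during the index stay has nearly complete follow-up, so a simple proportion suits it. Death over a year need not, yet it gets the same estimator. A subject who leaves alive at Day 60 stays in the denominator and counts as a survivor for ten unobserved months. The proportion can only be pulled down by this, and its interval treats that subject as fully observed.

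For re-occlusion, status *at* Day 365 and occurrence *up to* Day 365 are different quantities. Section 4.6 allows a re-occluded segment to be revascularized while its subject stays in the study, so a segment can have an event within the year and still be open at its end. Without a stated denominator, a reader of the final report cannot tell which quantity was estimated or which way it errs.

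**Working it through.** The protocol states no figure for one-year death, re-occlusion or dropout, so there is nothing of its own to reproduce on this point. The event risk F and one-year dropout d below are assumptions shown as ranges.

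**Death.** Take a constant event hazard and independent dropout spread evenly over the year, with l = -ln(1-F) and m = -ln(1-d). The expected crude proportion over all subjects is

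crude = l/(l+m) × [1 - (1-F)(1-d)].

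Example, F = 5% and d = 20%: l = 0.0513, m = 0.2231, so crude = 0.0513/0.2744 × (1 - 0.95 × 0.80) = 0.187 × 0.24 = 4.49%.

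| True one-year risk | d = 5% | 10% | 20% | 30% |
|---|---|---|---|---|
| 2% | 1.95% | 1.90% | 1.79% | 1.68% |
| 5% | 4.88% | 4.75% | 4.49% | 4.21% |
| Relative bias | -2.5% | -5% | -10% | -16% |

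For a rare event, crude/F is close to the observed share of follow-up, d/[-ln(1-d)]: 0.949, 0.896 and 0.841 at d = 10%, 20% and 30%. This is where the rule of about half the dropout fraction comes from.

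Timing matters. If all dropout fell at Day 30, crude = (1-d)F + d[1 - exp(-l × 30/365)]. A true 5% would then read 4.54% at d = 10% and 4.08% at d = 20%, a relative bias of -9% and -18%. With no dropout there is no bias.

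**Re-occlusion.** Take an assumed true cumulative risk of 20% and the same model, and vary only the denominator:

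| Denominator | d = 10% | d = 20% |
|---|---|---|
| All segments, unobserved counted as no re-occlusion | 19.0% | 18.0% |
| Only segments with a Day-365 duplex | 20% | 20% |
| Segments with an observed event or a completed year | 20.9% | 22.0% |

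At d = 20%, l = m, so the first row is 0.5 × (1 - 0.80 × 0.80) = 0.18. The third row is 0.18/(0.18 + 0.64) = 0.2195. The second row equals the true risk if dropout is unrelated to re-occlusion. The protocol does not state which row applies.

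**The case against.** A reader might infer that both one-year rates are biased low because withdrawn subjects stay in a full analysis set as event-free. The documents do not support that for re-occlusion. The Efficacy Segment Set already excludes segments that could not be crossed and those without a Day-30 Villalta score. Section 3.2.1 requires absence to be documented by duplex, so a segment with no Day-365 scan has no documented absence. Summaries by time point fit an observed-case denominator at least as well. The direction is therefore open, and this part of the objection stands.

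On death, the case against is that it does not matter. Death is not among the safety endpoints in section 3.3, is reported secondarily, and has no hypothesis or threshold. Subjects with a life expectancy under one year are excluded. For a true 2% risk and 10% dropout, the shift is from 4.0 to 3.8 expected deaths in 200. A 95% Wilson interval for 4/200 runs from about 0.8% to 5.0%, far wider than the shift. This limits the severity but does not make the estimator right.

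Finally, section 6.2.1 defers further detail to the statistical analysis plan, which is not shown. Denominators and censoring rules for re-occlusion may be settled there. However, the protocol itself fixes the estimator and set for death, and the mismatch between sections 3.2.1 and 6.2.2 is in its own text.

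**Conclusion.** For death the point holds. The planned one-year proportion is too low whenever subjects leave alive and their later deaths go uncaptured. The relative size is about half the dropout fraction if dropout is even over the year, and more if it is early.

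For re-occlusion, what holds is narrower: the endpoint and its analysis name different quantities, and a crude cumulative rate could err in either direction. All sizes rest on assumed dropout and event rates and on dropout unrelated to outcome. If sicker subjects leave, a censored estimate would be biased too, though it would no longer count unobserved time as event-free. Both outcomes are descriptive, so the severity is minor.

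**What to change.** **Section 6.2.3.** Report death as a Kaplan-Meier estimate at Day 365 with a 95% confidence interval, censoring at last contact and stating the time origin. Keep the crude counts alongside.

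**Sections 3.2.1 and 6.2.2.** Decide between status at 365 days and occurrence up to 365 days, and use one wording in both places.

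- If status at Day 365 is meant, state the denominator and how a revascularized segment counts.
- If the cumulative quantity is meant, report a cumulative incidence estimate at Day 365 with death as a competing event, censoring at the last duplex. Kaplan-Meier is not suitable here because it would treat death as censoring. The method should allow for re-occlusion generally being detected only at scheduled duplex visits, and for two limbs per subject, as section 6.2.1 already requires in general.
- In either case, give the number of segments with a Day-365 duplex.

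**Cost.** Wording changes and a little programming. The scheduled duplex visits and event-onset dates are already collected, and section 6.2.2 already plans a time-to-event analysis for healthcare use. The reported death rate will be slightly higher.

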6.2.3 Safety Analysis

Safety analyses will be performed for the Safety Subject Set.

For the primary safety analysis, the number and percentage of subjects with major bleeding within 72 hours of initiation of EkoSonic® Treatment will be reported with a 95% Wilson confidence interval.

Secondarily, the frequencies and proportions of subjects with symptomatic PE (diagnosed using CTPA, SPECT VQ, etc.) during hospitalization for the study procedure, and death during the 365 day follow-up period will be reported with 95% confidence intervals.

In addition, adverse events experienced will be mapped to standard terms and summarized. For a given event, the frequency and proportion of subjects reporting it will be tabulated according to the worst severity experienced. Separate tables will be constructed for (a) all reported events, (b) events judged as related to the study procedure/device/medications, and (c) SAEs.

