VCSS	X				X	X	X	X	X
SF-36	X				X	X	X	X	X
VEINES-QOL	X				X	X	X	X	X
Venography		X ⁵	X ⁶						
Leg Circumference	X				X	X	X	X	X
Review of Treatment Compliance & Exercise					X	X	X	X	X
Adverse Events			X	X	X	X	X	X	X
Concomitant medications	X				X	X	X	X	X

¹ Duplex ultrasound within 60 days prior to treatment or venography (Pre- EkoSonic® Treatment) will be performed to confirm persistent chronic DVT causing restrictive flow

²To be performed within 24 hours of the completion of treatment

³Test results may be obtained within 30 days prior to study treatment, unless otherwise specified in the exclusion criteria

⁴To be performed within 24 hours prior to the start of treatment

⁵ To be performed pre- and post-venoplasty

⁶To also be performed post- adjunctive treatment

C. ACRONYMS AND ABBREVIATIONS

AE	Adverse event
aPTT	Activated partial thromboplastin time
CBC	Complete blood count
CEAP	Clinical, Etiologic, Anatomic, Pathophysiological
CFR	Code of Federal Regulations
CFV	Common femoral vein
CPK-MB	Creatine Phosphokinase-MB
CPR	Cardiopulmonary resuscitation
CT	Computed tomography
CTPA	Computed tomography pulmonary angiogram
DIC	Disseminated intravascular coagulation
DVT	Deep vein thrombosis
eCRF	Electronic Case Report Form
ECS	Elastic compression stockings
FTC	Failure-to-Cross
FDA	Food and Drug Administration
GI	Gastrointestinal
ID	Identification
IDDC	Intelligent Drug Delivery Catheter
INR	International normalized ratio
ITT	Intention-to-treat
IVC	Inferior vena cava
MDR	Medical Device Reporting
MRI	Magnetic Resonance Imaging
MRV	Magnetic resonance venography
MSD	MicroSonic Device
PCB	Pneumatic compression boots
PCS	Physical component summary
PE	Pulmonary Embolism
PP	Per protocol
PTS	Post-thrombotic syndrome
PTT	Partial thromboplastin time
QoL	Quality of Life
rt-PA	Recombinant tissue plasminogen activator
SAR	Serious adverse reaction
SAE	Serious adverse event
SF-36	Short Form 36
SPECT	Single positron emission computed tomography
VEINES-QOL	Venous Insufficiency Epidemiological and Economic Study- Quality of Life
VCSS	Venous Clinical Severity Score
VVI	Venous Volumetric Index
VQ	Ventilation-perfusion

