4.2.6 Follow-Up Visits and Early Termination

At each of the follow-up visits: **Days 30± 7 days, 90± 10 days, 180± 14 days, 365 ± 14 days and at early termination**, the following assessments shall be performed:

- Duplex imaging
- Villalta scale (both legs)
- CEAP classification(both legs)
- VCSS (both legs)
- SF-36
- VEINES-QOL
- Leg circumference (both legs)
- Review of compliance with anticoagulant therapy, ECS, and exercise
- Serious Adverse and bleeding events
- Concomitant medications

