5.7 Documentation of adverse events

AEs shall be reported when noted during the hospitalization for the initial treatment and in the subject's medical record through the 30 day follow-up period. Subjects shall be encouraged to report AEs spontaneously or in response to non-directed questioning by their usual healthcare providers (for example, in response to the question "How has your health been since you last visit?"). If it is determined that an AE has occurred, the study staff member entering data into the eCRF should obtain all of the information necessary to complete the AE section.

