5.8 Reporting and duration of AE reporting period

Because the EkoSonic® Endovascular System is a commercial medical device, Investigators will comply with any hospital user reporting requirements. All observed or reported AEs including type of event, severity and relationship to the procedure, device use, thrombolytic and anticoagulant drug use will be recorded in the eCRF during hospitalization and through

30 day follow-up. At subsequent visits, SAEs and AEs related to venous thromboembolism or the EkoSonic® treatment will be collected.

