5.10 Specific reporting guidelines

Study Investigators should adhere to the following guidelines to ensure the quality and precision of AE reporting:

Use recognized medical terms.

Avoid the use of colloquialisms and non-standard abbreviations

If known at the time of AE reporting, a diagnosis should be reported instead of individual symptoms and signs (for example, record only “pneumonia” rather than “productive cough” and “elevated white blood cell count”).

If the reported symptoms and signs cannot be medically characterized as a single diagnosis or syndrome at the time of AE reporting, the information that is available should be reported. If a diagnosis is subsequently established, it should be reported as follow-up information as described earlier.

A cascade of clinical events (such as sequelae of an adverse event) should be identified as the primary, causative event. The cascade of events can be further described in the primary AE narrative. For example, when recording a death, the event or condition that caused or contributed to the fatal outcome should be reported as the serious adverse event. If the cause of death is unknown and cannot be determined at the time of reporting, “unknown cause of death” should be recorded as the adverse event.

Any AE potentially related to the study procedure that results in inpatient re-hospitalization or prolongs the index hospitalization (for study treatment) should be reported as a SAE. If a subject is re-hospitalized to undergo a medical or surgical procedure as a result of an AE, the event responsible for the procedure (not the procedure itself) should be reported as the SAE. For example, if a subject is re-hospitalized to undergo exploratory surgery as a result of a major bleeding event, record the major bleeding event that necessitated surgery as the SAE.

All observed or reported serious bleeding events occurring through the 365 day follow-up period, must be recorded.

Previously scheduled hospitalizations required for diagnostic or elective surgical procedures for the management of unchanged pre-existing medical conditions shall not be considered AEs.

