5.13 Expedited reporting of serious adverse events

Any AE that is considered serious must be reported to the device manufacturer, EKOS Corporation, within 24 hours of the site's knowledge of the event throughout the study via the e-mail address [REDACTED]

At the time of Sponsor notification, the Investigator shall enter into EDC as much of the information listed below as possible.

- a. Subjects demographics
- b. Pre-existing conditions
- c. The adverse event's description
- d. Date and time of AE onset
- e. Severity
- f. Treatment
- g. Results of diagnostic testing
- h. Duration of sequelae

- i. Outcome (if known)
- j. Information on suspected medications including dose, route of administration, frequency, dates, lot number, expiration date, and concomitant medications

When a SAE is reported, the device must be retained and returned to EKOS (see above for address for return devices). The EKOS representative may contact the Investigator to collect additional information on the EkoSonic® System.

When reporting a death, the primary event or condition that caused or contributed to the fatal outcome should be reported as the serious adverse event. Death would be reported as the outcome of the serious adverse event. If the cause of death is unknown at the time of reporting, report "unknown cause of death".

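### The 'all reported events' table in Protocol 6.2.3 has no time window, although non-serious adverse events are collected in full only to about Day 30 and serious ones to Day 365

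*Protocol*

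**What the plan says.** **Collection.** Protocol 5.7: "AEs shall be reported when noted during the hospitalization for the initial treatment and in the subject's medical record through the 30 day follow-up period". Section 5.8 repeats this for the eCRF and then narrows it: "At subsequent visits, SAEs and AEs related to venous thromboembolism or the EkoSonic® treatment will be collected". Serious events run for the whole study: 5.13 asks for SAE reports "within 24 hours of the site's knowledge of the event throughout the study", and 5.10 adds "All observed or reported serious bleeding events occurring through the 365 day follow-up period, must be recorded".

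**Tabulation.** Protocol 6.2.3: "For a given event, the frequency and proportion of subjects reporting it will be tabulated according to the worst severity experienced". Three tables are named: (a) all reported events, (b) events judged related to the procedure, device or medications, and (c) SAEs. None has a time window. The other safety measures in 6.2.3 each have one: 72 hours for major bleeding, the index hospitalization for pulmonary embolism, and 365 days for death.

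**Other statements on what is collected later.** The follow-up visit list in 4.2.6 names "Serious Adverse and bleeding events" at every visit. The schedule of assessments has an unrestricted row, "Adverse Events X X X X X X X", marked from post-treatment through Day 365 and early termination.

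**The concern.** A percentage in an AE table is normally read as the share of subjects who had the event over a stated period. In table (a) no single period applies. For a term that is not related to VTE or the EkoSonic treatment, a mild occurrence in month four is not collected, while an occurrence of the same term that leads to hospital admission in month four is. Both types feed one percentage per term.

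Two things follow. The percentage is neither a 30-day nor a 365-day incidence. And the omission runs one way, because late non-serious events are dropped and late serious ones are kept.

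Safety is part of the primary objective (3.1), the study has one arm, and the introduction says the data will support a journal publication. Absolute AE percentages are therefore what readers will take away, with no control arm showing the same artefact.

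**Working it through.** The protocol states no AE rate, so there is no figure of its own to reproduce. The check has two parts.

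**1. Coverage, from the text.** The Day 30 visit has a window of ±7 days (4.2.6).

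- Full AE collection: 30/365 = 8.2% of planned follow-up (23/365 = 6.3% to 37/365 = 10.1%).
- SAEs: 365/365 = 100%.

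Effect by table in 6.2.3:

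- (a) All reported events: affected for terms outside the later list in 5.8.
- (b) Related events: affected only for non-serious events related solely to the medications or to procedures other than EkoSonic. Those related to EkoSonic are still collected to Day 365.
- (c) SAEs: one window, not affected.

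**2. Size, on assumed rates.** These inputs are assumptions, not figures from the protocol:

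- a = 0.30 non-serious events per subject over 365 days (unrelated to VTE or EkoSonic);
- b = 0.10 serious events per subject over 365 days;
- f = share of the year's non-serious events that falls in the first 30 days;
- event counts are Poisson.

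Formulas:

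- True serious share of events: b/(a + b) = 0.10/0.40 = 25%.
- Serious share as collected: b/(af + b).
- Subjects with any event, as collected: 1 − exp(−(af + b)).
- Subjects with any event, full year: 1 − exp(−0.40) = 33.0%.
- Subjects with any event to Day 30, if serious events follow the same time pattern: 1 − exp(−0.40f).

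| f | Serious share as collected | Any event, to Day 30 | Any event, as collected | Any event, full year |
|---|---|---|---|---|
| 30/365 = 0.08 (even spread) | 80% | 3.2% | 11.7% | 33.0% |
| 0.25 | 57% | 9.5% | 16.1% | 33.0% |
| 0.50 | 40% | 18.1% | 22.1% | 33.0% |
| 0.75 | 31% | 25.9% | 27.7% | 33.0% |
| 0.90 | 27% | 30.2% | 30.9% | 33.0% |

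Example for f = 0.50: share 0.10/(0.15 + 0.10) = 40%; as collected 1 − exp(−0.25) = 22.1%; to Day 30 1 − exp(−0.20) = 18.1%.

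For non-serious events alone, a full year gives 1 − exp(−0.30) = 25.9% of subjects. As collected, the figure is 2.4% under an even spread and 23.7% at f = 0.90.

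With a common window to Day 30 and the same time pattern for both types, the serious share is bf/(af + bf) = 25% at every f. The distortion therefore comes from the unequal windows.

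**The case against.** **This is table layout, which belongs in the SAP.** Section 6.2.1 leaves further analysis details to an SAP that is not shown. Section 6.2.3 never says that table (a) estimates one-year incidence, and a table of all reported events is literally what 5.8 would produce. This has weight and keeps the point minor. It does not remove it, because 6.2.3 itself fixes the statistic, the severity rule and the three tables, and omits a window only where the inputs have mixed windows.

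**Severity is not seriousness.** This stands. Section 5.12 grades mild, moderate and severe; 5.3 defines serious separately, by outcome. A reader might infer that worst severity moves toward serious by construction. The protocol does not support that, since serious is not a grade in the table. The shift in grades is indirect, to the extent that serious events tend to be graded more severe. The serious share of events used above measures the imbalance; no planned table reports it.

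**Risk is not constant after a one-time procedure.** This also stands. A reader might extrapolate a 20% Day 30 proportion to 1 − 0.80^(365/30) = 93% at one year. Nothing in the protocol supports such a rate: 5.9 says alteplase bleeding is most likely within 24 hours and very unlikely after 72, and Table 1 lists events anticipated during treatment. The early-clustering rows of the table are the more plausible ones for procedural terms, and the even-spread row is an upper end.

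**The gap may be narrower.** Section 4.2.6 arguably adds bleeding events at every visit, and the schedule of assessments marks AEs without restriction. Neither matches 5.8, so the loss could be smaller than 5.8 implies. The disagreement itself needs settling.

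**Conclusion.** The point holds as a minor, descriptive one. Followed as written, 6.2.3 produces percentages in table (a) that mix about 30 days of non-serious events with 365 days of serious ones for terms outside the later list in 5.8. The direction is fixed. The size is not known from the documents: on the assumed rates, a true serious share of 25% appears as 27% if 90% of non-serious events fall in the first 30 days, 40% if half do and 80% under an even spread. It becomes small only if nearly all non-serious events occur by Day 30. This takes 5.8 as the rule for what is collected after Day 30.

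A reader might infer that the trial's safety conclusions are compromised. The protocol does not support that. Major bleeding within 72 hours and in-hospital pulmonary embolism fall where all AEs are collected, deaths are collected to Day 365, and the SAE table has one window. With a single arm, no between-group comparison is biased. Table (b) is touched only in the part described above. The ±7-day visit window is ordinary and has a negligible effect.

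**What to change.** In 6.2.3, replace table (a) with two tables:

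1. All AEs by worst severity, from treatment through the Day 30 visit.
2. Only the categories collected throughout (SAEs, VTE-related AEs and EkoSonic-related AEs), from treatment through Day 365.

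State the window in every AE table title. Split the affected part of table (b) in the same way, that is, non-serious events related solely to the medications or to non-EkoSonic procedures.

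Reconcile the schedule of assessments, 4.2.6 and 5.8 on what is collected after Day 30, so that the second table's content is defined by a single rule.

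Cost: a wording change and one or two extra tables. No new data are needed.
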